3.5.5. MISSING DATA, SENSITIVITY ANALYSES AND ACCOUNTABILITY TABLES

Data will be considered "missing" for a given primary endpoint if this endpoint cannot be calculated or is not available for a subject. If the subject has had a device failure or a UADE at any point or prior to their 22+ month outcome, they will not be considered as missing data for the Absence of Revision/Removal/UADE endpoint, as this endpoint is cumulative. A subject who has had a revision prior to two years will be considered a radiographic failure at the two - year time point for purposes of the primary analysis. When possible (i.e. the subject is seen by a study investigator in a non-emergency situation and collection of the data will not cause undue burden), Knee Society Scores will be collected for these subjects before the revision is performed in order to prevent these patients from missing knee scores in the primary efficacy analyses. A "worst case" score of twelve will be given for any Knee Scores that cannot be collected prior to the revision procedure. As an attempt to minimize missing data from the remaining primary endpoints, a nextobservation-carried-backward approach will be used to impute values for subjects missing data. Under this approach, if a primary endpoint is missing at the 24 month visit, the subject's next observation post 24-months will be used to impute a 22+ month outcome for that subject, for that particular endpoint. If no data is available after 2 years to carry backward for the missing data point, the subject's latest observation pre-24months will be carried forward to impute values for the missing 24 month visit.

Sensitivity analyses will examine the sensitivity of the results to missing values of the primary outcomes using a tipping point analysis, a best-case analysis, a worst-case analysis, and an analysis that imputes missing data with the last observation carried forward. If sensitivity analyses do not agree and we have more than 15% of values missing in either group, the method of Multiple Imputation may be used to further investigate the sensitivity of results to the missing data.

Accountability tables will be generated to show, at each study visit, the number of subjects who might be expected to attend a given visit and the number and proportion who did attend. Rows of the table will show counts for subjects contributing all data needed to

create the primary, binary composite outcome and subjects contributing only some of the components of that outcome.

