2.7.4 TABLE OF FOLLOW-UP INTERVALS

INTERVAL	FOLLOW-UP WINDOW	MONTHS POST- OP RANGE	DAYS POST-OP RANGE
6 week follow-up	± 3 weeks	1-2	21-63
6 month follow-up	± 1 month	5-7	153-214
1 year follow-up	± 2 months	10-14	304-426
2 year follow-up	± 2 months	22-26	669-791
*3 year follow-up	± 2 months	34-38	1035-1157
*4 year follow-up	± 2 months	46-50	1400-1522
*5 year follow-up	± 2 months	58-62	1765-1887

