2.12 END OF ROUTINE STUDY ASSESSMENT

Discontinuation/Withdrawal and Post-Routine Exploratory Patients will be recorded on a Study Completion eCRF (SC100). This case report form is completed when the patient completes the study according to the protocol or if there is a change to the active participation of a patient in the study. Examples include lost-to-follow-up, death, or subject removal of informed consent.

Patients who have had an UADE or a Revision and/or Removal of any Device Component should be followed for safety and patient outcomes according to the visits indicated in this protocol (if possible), for the duration of the study. These patients are considered Post-Routine Exploratory Patients.

_

^a Robertsson, Otta, et al. *Patient Satisfaction Compared With General Health and Disease-Specific Questionnaires in Knee Arthroplasty Patients*. Journal of Arthroplasty, 2001, pp 476-482.

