3.1.1. RADIOGRAPHIC SUCCESS

The proportion of radiographically successful knees in the Cementless group is non-inferior to the proportion of radiographically successful knees in the Control group using an 8% margin of non-inferiority. The test is based on the upper bound of a one-sided 95% confidence interval for the difference, Control minus Cementless, of proportions of success at 22+ months. A conclusion of non-inferiority is supported if the upper bound of the confidence interval is 0.08 or less. In addition, a Fisher's Exact p-value will also be computed to test this hypothesis.

In this analysis, each knee will be considered as a separate case, and unilateral and bilateral subjects will be analyzed together, providing the unilateral and bilateral groups are poolable per sensitivity analyses given in Section 3.1.5°.

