3.3 SAMPLE SIZE JUSTIFICATION

In order to calculate the sample size for this study, the sample size needed to obtain 90% power for each primary endpoint was calculated. The endpoint requiring the largest sample size to maintain 90% power was Radiographic Success. Therefore, this is the sample size used in this study to ensure that we have a sufficient number of knees/patients to test each of the four primary endpoints with at least 90% power.

The sample size for the radiographic success primary endpoint was calculated as follows:

Let p_I and p_C denote the true population proportions of a successful outcome in the Cementless and Control groups, respectively.

Under H_0 , p_C is markedly larger than p_I and the Cementless device is inferior. Contrarily, under H_1 , this is not true and the true proportion of success for the Cementless device is, at worst, δ less than for the Control. We have δ = 0.08 (i.e., 8%).

Information about plausible values of the proportions p_I and p_C is available in the SSED for the LPS Flex Mobile Device (PMA #P060037). This document was used to help estimate the percentage of radiographic success for sample size purposes because it used a similar radiographic success/failure endpoint as the one given in this protocol. For purposes of the sample size calculation, we use the radiographic failure rates in Table 5 (page 18-19) of the document. This shows a 1.2% radiographic failure rate for the investigational device and a 2.4% radiographic failure rate for the control. Since we have slightly different radiographic success criteria, and because we want to ensure that we have adequate power for testing this endpoint, we will use 5% as our estimate of radiographic failure, giving a 95% estimate of radiographic success.

Assuming 95% to be the true, equal values of p_1 and p_2 , non-inferiority sample size calculations were implemented in nQuery Advisor 7.0 software using a 2:1 ratio of Cementless to Control subjects. This software uses methodology as described in an article by Farrington and Manning^e.

Definitions:

 p_l : Proportion of successes in the Experimental (Oxford Cementless) treatment group.

 $p_{\mathcal{C}}$: Proportion of success in the Control (Oxford Cemented) treatment group.

For a specified constant, $0 < \delta < 1$, the hypotheses of non-inferiority are:

$$H_0: p_C - p_I > \delta \text{ vs. } H_1: p_C - p_I \leq \delta.$$

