3.5.4. Analyses of Secondary Outcomes

These outcomes include the primary study endpoints at times other than two years. In addition, a composite success/failure endpoint consisting of the four primary outcomes will be tested for non-inferiority, Cementless vs. Control, using a non-inferiority margin of 10%. In this composite, the threshold for success for the Knee Society Assessment and Function scores will be 80 points. A composite success outcome requires a successful outcome for all four components.

In addition, at all-time points, implant revisions or removals will be described by Kaplan-Meier time-to-failure curves and compared using log-rank tests. Mean Knee Society Assessment Score, Knee Society Function Score, and Oxford Knee scores will be displayed by time point and compared between treatment groups. Analyses will be performed using standard statistical tests and will be chosen as appropriate for the scale and distribution of

the measures being analyzed (chi-square, Cochran-Mantel-Haenszel chi-square, Student's t).

Bilateral patients will be analyzed as a separate group for purposes of secondary analyses of Knee scores at each time point as well in the secondary analysis of composite success rates. For other analyses, including radiographic and safety outcomes, bilateral and unilateral patients will be analyzed together.

Secondary outcomes will be analyzed using all patients with available data for the endpoint being analyzed. As with the primary analysis, the secondary analyses will use the device that was actually implanted if it was a study device; if a study device is not received, the patient will not be included in the secondary analyses.

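### Films and scores taken after a revision can enter the analysis: carry-backward is not barred at a revision after two years, the failure rule has wording gaps, and secondary visits have no revision rule

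*Combined protocol and SAP*

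**What the plan says.** Post-revision data will exist. Under Section 2.12, patients with a UADE, revision or removal "should be followed for safety and patient outcomes according to the visits indicated in this protocol", where possible, to the end of the study. They are labelled exploratory, but no part of the SAP attaches an analysis rule to that label.

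Section 3.5.5 has a revision rule for the primary analysis. A subject revised before two years is a radiographic failure at two years. That subject's knee scores are those taken before the revision, or twelve if none could be taken. For the remaining missing primary values, "the subject's next observation post 24-months will be used to impute a 22+ month outcome for that subject". If there is no later observation, the latest earlier one is carried forward.

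Section 3.5.4 covers the secondary analyses: "Secondary outcomes will be analyzed using all patients with available data for the endpoint being analyzed". Knees are grouped by the study device actually implanted, and no revision rule is given.

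Two other places matter. Section 2.5 defines removal (the whole configuration comes out) separately from revision (part of it comes out). Section 2.7.4 sets the two-year window: "2 year follow-up ± 2 months 22-26 669-791".

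**The concern.** Once a component has been exchanged or taken out, a later knee score no longer describes the original construct alone. A later film may show a component that was not there at six weeks, although Section 3.0 judges migration against the six-week films. The plan accepts this principle for revisions before two years. Where its wording stops short, a knee whose device was revised or removed can supply a good film or score to the arm of that device. At stake are three of the four co-primary endpoints (radiographic success and the two Knee Society scores), to a small extent, and the secondary Knee Society, Oxford, satisfaction and radiographic results, to a larger one.

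**Working it through.** **1. The plan's own figure.** Inputs: one-sided 5% (Section 3.1.1: "The test is based on the upper bound of a one-sided 95% confidence interval for the difference, Control minus Cementless"); 90% power (Section 3.3: "the sample size needed to obtain 90% power for each primary endpoint was calculated"); 95% success in both arms (Section 3.3: "we will use 5% as our estimate of radiographic failure, giving a 95% estimate of radiographic success"); margin 0.08 (Section 3.1.1: "using an 8% margin of non-inferiority"); allocation 2:1.

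Control knees = (1.645 + 1.282)² × (0.95 × 0.05) × (1 + 1/2) / 0.08² = 95.3, so 96. Cementless = 2 × 95.3 = 190.7, so 191. With the 10% and 15% allowances taken together, 191/0.75 = 254.7, so 255, and 96/0.75 = 128. The stated 191/96 and 255/128 reproduce. The point does not affect sample size.

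**2. The rules applied to four knees.** The window's midpoint is (669 + 791)/2 = day 730.

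| Knee | What the text gives |
|---|---|
| 24-month visit missed, revised at month 30, seen at month 36 | Not revised before two years; the month-36 observation is carried back |
| Revised on day 740, seen on day 785, in window | Not clearly before two years; the day-785 film and scores can be used directly |
| All components removed before two years | The radiographic-failure rule names revision only |
| Revised at month 4, seen at 6 months and 1 year | Failure rule limited to the primary analysis; both visits count as available secondary data |

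**3. Primary analysis, per knee.** One knee read as a success instead of a failure moves radiographic success by 1/191 = 0.52 points (Cementless) or 1/96 = 1.04 points (Control). This is a maximum: it assumes a successful post-revision film and a failure otherwise. For a knee score, replacing twelve by 80 (80 is assumed) moves a mean over 191 Cementless knees (assumed) by (80 − 12)/191 = 0.36 points, against margins of 6.4 and 9.2.

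**4. Primary analysis, how many knees.** The documents give no rates for this. Assume that 5–15% of knees miss the 24-month visit and that 0.5–3% have a first revision in year three. Expected knees = arm size × missed × revised:
- Cementless: 255 × 0.05 × 0.005 = 0.06, up to 255 × 0.15 × 0.03 = 1.15.
- Control: 128 × 0.05 × 0.005 = 0.03, up to 128 × 0.15 × 0.03 = 0.58.
- Share of an arm: 0.025 to 0.45 percentage points.

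This is generous, because it gives every such knee a later visit. Annual visits stop once the last patient reaches two years. It sizes the first knee in the table only; the window and removal gaps are not counted.

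**5. Secondary visits.** Assume that 1–5% of an arm has been revised by a given visit. If all their films are read as successes, that arm's radiographic success rises by up to 1–5 points. If their scores are 70–85 (assumed) and not twelve, the arm mean rises by 0.01 × (70 − 12) = 0.6 up to 0.05 × (85 − 12) = 3.7 points. With 3% revised and a 40-point gap (both assumed), it rises by 0.03 × 40 = 1.2 points.

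**6. Direction.** The comparison moves only by the difference between arms. With equal revised shares and equal post-revision results, the shifts cancel. With 3% in one arm and 1% in the other, the radiographic difference moves by up to 3 − 1 = 2 points, in favour of whichever arm has more revisions.

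**The case against.** A reader might infer that the plan has no cut-off at revision at all. It does: the sentences just before the carry-backward rule set one for revisions before two years. A reader might also infer that failures are hidden. They are not. Revision, removal or UADE is a co-primary endpoint of its own, the Kaplan-Meier curves count revisions and removals, and the composite requires success on all four components. Nor do the documents support a claim that the gaps favour non-inferiority, since the direction depends on which arm has more affected knees. The plan is silent on post-revision data; it does not direct that they be credited to the device.

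Further points carry weight:
- The missed-visit knee has a missing value, so the planned tipping-point, best-case, worst-case and last-observation-carried-forward analyses would examine it.
- Two years may mean the two-year visit. Section 3.4.1 speaks of a revision at or before the 22+ month visit, though it concerns who is included and not how they are scored.
- Revision may be shorthand that covers removal. Section 3.2 shortens the name of the co-primary endpoint in the same way.
- A revision can be a bearing exchange. The bearing is the same in both systems, and the femoral and tibial components may stay in place, so later films can still inform on fixation.
- Scoring a knee that was intact at 24 months and revised at month 30 as a 24-month failure would be a debatable choice of estimand.

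These points limit the size of the concern and shape the remedy. They do not supply the missing rules: sensitivity analyses do not define the primary value, and the exploratory label removes no data.

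**Conclusion.** The point holds in a limited form. The 24-month primary analysis is protected for revisions before two years. It is not protected against carrying back an observation made after a later revision or removal, and its failure rule is incomplete on removal and on revisions late in the window. Secondary time points have no rule for the scores and films.

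The effect on the primary analysis is small: at most 0.52 or 1.04 points per knee, and for the carry-backward gap about one Cementless knee or fewer and at most 0.45 points per arm, against an 8-point margin. This rests on assumed missed-visit and revision rates. Within-arm secondary figures could be overstated by 1–5 points of radiographic success and 0.6–3.7 score points, again under assumed rates. Neither range is a bias in the comparison unless the arms differ. The reason to act is that the choice should be fixed before revisions by arm are known.

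**What to change.** 1. In Section 3.5.5, state that no observation made after a revision or removal is carried backward. If the next observation is post-revision, use the latest pre-revision observation through the plan's existing carry-forward step. A knee revised at month 30 then does not become a 24-month failure for that reason alone.
2. In the same section, change the trigger of the failure and knee-score rule to: *revision or removal before the observation used for the 22+ month outcome, when that visit falls in the 2-year window*.
3. In Section 3.5.4, count a revised or removed knee as a radiographic failure from the date of that procedure, in line with the primary rule. Report post-revision knee scores, Oxford scores and satisfaction separately. Keep an all-available-data analysis as a sensitivity analysis, which retains films taken after a bearing exchange.

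The cost is SAP wording and a date filter in programming. No new data are needed and the sample size does not change. Some secondary figures may be slightly less favourable.

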2.5 STUDY DEFINITIONS

Adverse Event (AE): Any untoward medical occurrence in a patient or subject in a clinical investigation. AEs may or may not have a causal relationship with the device. An AE can therefore be any unfavorable and unintended sign (including an abnormal laboratory finding), symptom, or disease temporally associated with the use of a product.

Design One patients: This is the term for the eleven (both control and investigational) patients enrolled in the study before the cementless (Investigational) tibial design was changed to modify the porous coating.

Design Two patients: This is the term for all patients (both control and investigational) enrolled after the cementless (Investigational) tibial design was changed to modify the porous coating.

Discontinuations: Patients who are lost to follow-up, die or formally withdraw (in writing) their consent to additional follow-up.

Failures: In the patient accounting tables, this represents number of subjects who meet the definition of patient failure at the listed window interval.

Missing Data: Patients who refuse to return for follow-up or who cannot be located and therefore do not formally withdraw consent – also described as "lost to follow-up." Sites will be instructed to continue efforts to contact these patients. See *Missing Data, Sensitivity Analyses and Accountability Tables* section for more information on how missing data will be handled in the analysis.

Osteolysis: Osteolysis is defined as a progressive radiolucency of >3mm in *two or more contiguous zones* not present on 6 week follow up radiographs and/or a bony destructive lesion that is progressive in nature.

Other Interventions: This category includes other surgeries the patient incurs while enrolled in the study that are seemingly unrelated to the implanted device. This would include surgeries such as cholecystectomy, appendectomy, coronary artery bypass surgery, etc.

Removal: A procedure where all of the original system configuration is removed.

Reoperation: Any surgical procedure that does not include removal or revision, for example, drainage of a hematoma at the surgical site.

8

Revision: A procedure that removes part of the original implant configuration, with or without replacement of the entire component configuration.

Serious Adverse Event (SAE): Any untoward medical occurrence that:

- Results in death
- Is life-threatening

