2.7.1 SCHEDULE OF EVENTS TABLE

FORM NAME	Form Number	Version	Pre-Op	Surgery	Immediate Post-Op	6 WK	6 MO	1 YR	2 YR	Annual*
Informed Consent	Per IRB		X							
Patient History Form & Record of Medications	HX100	2.0	x							
Patient Operation Forms	OP100 & OP200	2.0		X						
KSS Scoring Form	KSS100	2.0	X			X	X	X	X	x
Oxford Knee Scoring Form	Oxford100	4.0	X			X	х	х	x	X
Patient Satisfaction Questionnaire	SQ100	1.0				х	х	х	х	х
Radiographic Evaluation (Completed by Independent Radiograph Reviewer)	XR100	3.0				х	х	х	х	х
Protocol Deviation Form	PD100	2.0	As appropriate							
Adverse Event Form (Code List Form AE200)	AE100	4.0	As appropriate							
Study Completion (also capturing implant removals)	SC100	1.0	As appropriate							
Adverse Event Determination	AED100	1.0	As appropriate							

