2.11 PRIMARY AND SECONDARY STUDY ENDPOINTS

The study's primary safety and efficacy endpoints for the Oxford® Cementless Partial Knee System will include:

• Radiographic Success at 22+ months Study ID: ORTHO.CR.US30

- Absence of Revision/Removal/UADE at any time point
- The Knee Society Assessment Score at 22+ months
- The Knee Society Function Score at 22+ months

The study's secondary endpoints include:

- The Knee Society Assessment Score at all time points other than 22+ months
- The Knee Society Assessment Score for bilateral subjects at all time points
- The Knee Society Function Score at all time points other than 22+ months
- The Knee Society Function Score for bilateral subjects at all time points
- The Oxford Knee Score at all time points
- Radiographic Success at all other time points
- Single question assessment of patient satisfaction at all time points^a

The safety of the system will further be monitored by recording and reporting adverse events [including serious adverse events not considered UADEs throughout the follow-up period].

Safety data will be summarized as follows:

- Device removals or revisions
- Unanticipated adverse device events
- Systemic adverse events
- Local adverse events
- Reoperations and Other Interventions

Any patient who fails to return for multiple, consecutive, scheduled follow-up visits for any reason other than the criteria listed above will be identified as Missing Data.

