- a. Presence of osteolysis defined as a radiolucency that is both progressive and is greater than 3 mm at its maximum interface in *two or more* contiguous zones OR a bony destructive lesion that is progressive in nature.
- b. Migration/subsidence of any femoral or tibial component defined as a component migration/subsidence of > 3 mm as compared to 6 week radiographs.
- c. A component fracture

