3.4 ADDITIONAL STUDY POPULATION INFORMATION

3.4.1.PER PROTOCOL (PP) POPULATION

Patients who have complete data (i.e. at radiographic, clinical, and safety) collected per the protocol are the Per Protocol (PP) population. Those cases with complete data for a primary endpoint collected per the protocol at 22+ months or who have had a revision/UADE at or before the 22+ month visit will be used in the analysis of that primary endpoint.

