3.5.2. ANALYSES OF STUDY POPULATION

Analysis for primary and secondary endpoints will use the Per Protocol population, which consists of those cases with complete data for one or more of the primary endpoints collected per the protocol at the 22+ month follow-up visit (or, as described below in the section on Missing Data, at the last or next available visit if the primary endpoint in question is missing at the 24- month visit). The exception to this is the primary endpoint of Absence of Revision/Removal/UADE, which is cumulative; therefore all cases that have failed at or prior to 24 months due to a revision or UADE will be included in the analysis of that primary endpoint. For each primary endpoint, all available data will be used, even if the subject has missing data for one or more of the other endpoints. Since indications and inclusion/exclusion criteria are exactly the same for both device groups, and because randomization is received at the time of surgery, it is expected that few patients will fail to receive the assigned treatment. However, in the event that they do not, the primary analysis will use the device that was actually implanted if it was a study device; if a study device is not received, the patient will not be included in the primary analysis.

Bilateral patients will be used in the primary analysis for the of Radiographic Success and Absence of Revision/Removal/UADE endpoints, but will be analyzed separately for the Knee Society Function and Assessment endpoints. The bilateral patients will not be included in the primary analysis for the Knee Score endpoints, as there is no way to ensure that the knee scores for one knee will not be affected by the other. The sample size has been increased by 10% to allow for this, a percentage based on the bilateral enrollment in the post-approval study for the OxfordTM Menisal Unicompartmental Knee System.

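### The primary radiographic analysis can fill a missing 22+ month result from any earlier film, with the 6-week reference film not excluded; this can push that test's type I error above 5%

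*Combined protocol and SAP*

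**What the plan says.** Section 3.5.5 fills a missing 24-month primary endpoint in two steps. The next observation after 24 months is carried back. If there is none, "the subject's latest observation pre-24months will be carried forward to impute values for the missing 24 month visit". Section 3.5.2 admits such values to the Per Protocol set used for the primary analysis, with data taken "at the last or next available visit if the primary endpoint in question is missing at the 24- month visit".

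Section 3.4.1 defines the cases for each primary endpoint more narrowly: "Those cases with complete data for a primary endpoint collected per the protocol at 22+ months or who have had a revision/UADE" by that visit. It mentions no carried values.

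The radiographic criteria use the 6-week film as reference. Section 3.0 defines migration failure as "component migration/subsidence of > 3 mm as compared to 6 week radiographs". Section 2.5 requires an osteolytic radiolucency to be progressive and "not present on 6 week follow up radiographs". Appendix B (Baseline Evaluation) names the 6-week films as the radiographic baseline.

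A 6-week result will nevertheless be on file. The schedule in section 2.7.1 has "Radiographic Evaluation (Completed by Independent Radiograph Reviewer") from 6 weeks onward, and section 2.11 lists "Radiographic Success at all other time points" as a secondary endpoint.

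Safeguards in the plan:
- A knee revised before two years counts as a radiographic failure (3.5.5).
- Annual films continue until the last patient reaches two years (2.0), and they feed carry-backward first.
- Tipping-point, best-case, worst-case, carry-forward and ITT sensitivity analyses are planned (3.4.2, 3.5.5).

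**The concern.** A film that is its own reference cannot show migration or new radiolucency. Carrying it forward records a success and counts the knee as observed. In a non-inferiority comparison, masking the same share of failures in both arms shrinks a true deficit towards zero, which favours a false conclusion of non-inferiority. Carrying a 6-month or 1-year film does the same to a smaller extent, because some failures appear only later.

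The radiographic endpoint sets the sample size, and the study cannot succeed without it. An error in this test reaches the whole trial only to the extent that the other three endpoints are very likely to pass. The concern is limited to the radiographic endpoint.

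**Working it through.** **1. The plan's own sample size.** Inputs from sections 3.1.1 and 3.3: one-sided α = 0.05, power 90%, margin 0.08, success 0.95 in both arms, ratio 2:1. With unpooled variance,

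n_C = (1.645 + 1.282)² × (0.0475 + 0.0475/2) / 0.08² = 95.3, so 96 Control; 2 × 95.3 = 190.7, so 191 Cementless.

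This matches the plan. The Farrington–Manning formula gives 94 and 188, within 3%. Inflation also matches: 287/(1 − 0.25) = 382.7, so 383 (255 and 128).

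**2. Type I error with nothing carried.** The truth is set at the margin: failure 0.05 in Control and 0.13 in Cementless, n = 128 and 255. All pairs of binomial counts are enumerated, and the section 3.2 Wald bound is compared with 0.08. Exact type I error is 4.4%.

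**3. Adding carry-forward.** Let m be the share of knees carried and v the share of their failures visible on the carried film. The recorded failure rate is then f × [(1 − m) + m·v]. For m = 0.15 and v = 0, the rates are 0.0425 and 0.1105, and the apparent deficit falls from 0.080 to 0.068. The documents give neither m nor v, so both are assumptions. The 15% upper value is the attrition allowance in section 3.3.

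| Carried, each arm | 6-week film only (v = 0) | Half visible | 75% visible |
|---|---|---|---|
| 0% | 4.4% | 4.4% | 4.4% |
| 5% | 6.0% | 5.2% | 4.8% |
| 10% | 8.2% | 6.0% | 5.2% |
| 15% | 11.0% | 7.0% | 5.6% |

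The error passes 5% above about 2.0%, 4.0% and 8.0% carried, respectively.

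**4. Mixed films.** Some carried knees have only a 6-week film; the rest have films showing 75% of failures (1,000,000 simulations). Results at 5%, 10% and 15% carried:

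| 6-week-only share of carried knees | As written | 6-week-only knees left out |
|---|---|---|
| One half | 5.4%, 6.5%, 7.9% | 4.7%, 4.9%, 5.1% |
| One fifth | 5.0%, 5.7%, 6.4% | 4.8%, 5.1%, 5.4% |

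**5. Cases by arm.** At 15% equal loss, visibility of 75% in Cementless and 50% in Control gives 4.9%; reversed, it gives 7.9%. Loss of 5% in Cementless and 15% in Control, all 6-week-only, gives 4.2%. The direction is therefore not fixed.

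**6. Worked example, 10% missing.** Among observed knees, 19/230 Cementless and 5/115 Control failures give a bound of 0.0391 + 1.645 × 0.0263 = 0.082, which fails. With the missing knees carried as successes, 19/255 and 5/128 give 0.0354 + 1.645 × 0.0237 = 0.0745, which passes.

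**7. If loss depends on outcome.** Assume failing knees are lost twice as often, with equal total loss of 5%, 10% or 15% in each arm:

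| Films available | Carried | Left out | Multiple imputation |
|---|---|---|---|
| 6-week only | 7.5%, 12.4%, 20.1% | 5.7%, 6.9%, 8.8% | 5.6%, 7.0%, 9.2% |
| Later films, 75% visible | 5.0%, 5.7%, 6.5% | 5.6%, 7.0%, 9.0% | 4.8%, 5.1%, 5.5% |

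Imputation here draws by arm, conditional on the earlier film result (25 imputations, Rubin's rules, 200,000 simulations). If loss is unrelated to outcome, it gives 4.4% to 4.6%. Knees are treated as independent throughout.

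**The case against.** The strongest counter-reading is that section 3.5.5 calls data missing "if this endpoint cannot be calculated or is not available for a subject". A change from baseline with only the baseline film cannot be calculated, so a careful analyst might refuse to carry a 6-week film. That is possible, but those words define when the 22+ month endpoint is missing. They do not restrict which earlier observation fills it, and a scored 6-week result will exist. The film-reading rules in Appendix D are not in the public text.

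The conflict with section 3.4.1 is the weaker part. Section 3.5.2 refers to the missing-data section, so the intent can be inferred. Still, no text says which definition governs.

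The size is also open to challenge:
- The 6-week-only column needs every carried knee to lack any later film. Carry-backward and continuing annual visits make that uncommon, so the column is an upper bound.
- Known revisions are never masked. If half of the failures in each arm were known revisions (an assumption), 5%, 10% and 15% carried would give 5.2%, 6.0% and 7.0%.
- With one fifth 6-week-only, excluding those knees lowers the error by only 0.2 to 1.0 points.
- The worked example sits at the margin. With 18 Cementless failures instead of 19, both analyses pass (0.078 and 0.070).

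These points bear on weight; the rule as written remains. The planned tipping-point and worst-case analyses would expose a pass that depends on carried successes, but nothing ties them to study success. The carry-forward sensitivity analysis largely repeats the primary fallback. Multiple imputation is only optional, and only if the sensitivity analyses disagree and more than 15% of values are missing in either group.

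**Conclusion.** The concern holds and should be fixed; confidence is medium. The text permits a reading in which an unobservable failure is scored as an observed success in the primary analysis, and it leaves two definitions of the analysis set unreconciled. Under equal loss, the mixed-film cases put the error of the radiographic test between 5.0% and 7.9%, against 4.4% with nothing carried. The 11.0% figure is an upper-end case.

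The actual size and direction depend on three quantities that the documents do not give: the share carried, any difference in loss between arms, and how many failures already show on the carried film in each arm.

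**What to change.** Keep carry-backward, and change the following:

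1. State that the 6-week film is never an outcome observation in the primary radiographic analysis.
2. Reconcile sections 3.4.1, 3.5.2 and 3.5.5 on which knees enter that analysis.
3. Preferably, replace carry-forward of the 6-month and 1-year films with prespecified multiple imputation using arm, earlier film results and baseline, with a model suited to few events (for example penalised logistic regression). Keep carry-forward as a labelled sensitivity analysis, and name the tipping-point analysis as the key check.

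Steps 1 and 2 are the core and need only SAP wording. Step 3 adds some programming. Knees with later films should not simply be dropped: if loss depends on outcome, leaving them out does worse than carrying them, and imputation does best (working, step 7). For 6-week-only knees, imputation is no clear improvement on leaving them out. No option secures 5% in every case when loss depends on outcome.

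The cost is slightly wider intervals. Exact power at 95% success in both arms is 97.6% with none missing, 95.7% at 217/109 (15% left out) and 94% at 191/96, against the 90% target. Imputation at 15% missing gives 95.4%.
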